10.4.3 Data Listings

Data listings will be prepared for all subjects, including flags for any abnormal vital signs value or abnormal orthostatic measure at any time-point.

10.5 Physical Examination

The number and percentage of subjects having an abnormal physical exam at Screening, or with a change from Screening, will be summarized by body system for each treatment group, overall and by age group.

Physical examination findings at each evaluation will be listed for the safety dataset. Subjects with abnormal findings will be noted on the data listings.

11 Interim Analyses

No interim analyses are planned for this study.

12 Deviations from Protocol Analysis

The following are a list of changes and/or additions from the protocol specified analyses:

- In addition to the pre-specified 95% CIs, 90% CIs will also be computed and displayed.
- Additional summaries for pre-specified orthostatic changes in blood pressure will be provided.
- Pharmacokinetic concentration summaries and listings will be provided.

13 References

[1] Clinical Practice Guideline: Orthostatic vital sings full version. Emergency Nurses Association. December 2011.

14 Tables, Listings and Figures

The document with tables, listings, and figures (TLF) shells is presented in a separate document.

Appendix 1Markedly Abnormal Laboratory Safety Values andVital Signs

HEMATOLOGY					
Variable	Units	Age	Markedly Abnormal Criteria		
			Low (≤)	High (≥)	
Hemoglobin	g/dL	6 mo-18 yr	8	18	
RBC	$x10^{6}/mm^{3}$	6 mo-18 yr	3.5	6	
Hematocrit	%	6 mo-18 yr	30	50	
Reticulocytes	%	6 mo to 12 yr	NA	1	
		> 12 yr:	NA	2	
MCV	F1	6 mo-18 yr	70	100	
МСН	pg	6 mo-18 yr	20	35	
MCHC	g/dL	6 mo-18 yr	30	NA	
Leukocytes	$x10^{3}/mm^{3}$	6 mo to 18 yr	4	20	
Neutrophils	$x10^{3}/mm^{3}$	6 mo-18 yr	1	10	
Lymphocytes	$x10^{3}/mm^{3}$	2-18 yr	1	10	
Eosinophils	%	All ages	NA	5	
Monocytes	%	6 mo-18 yr	NA	5	
Basophils	0⁄0*	6 mo-18 yr	NA	1	
Platelets	$x10^{3}/mm^{3}$	6 mo-18 yr	50	750	

*The percentage indicates the relative number of each type of leucocytes in the blood. The absolute count is calculated by multiply the relative value (%) by the total leukocyte count/100.

CHEMISTRY					
Variable	Units	Age	Markedly Abnormal Criteria		
			Low	High	
ALT	U/L	1-19yr	Not applicable	\geq 3x NL	
AST	U/L	1-19yr	Not applicable	\geq 3x NL	
Total protein	g/L	> 1 yr	≤ 40	≥80	
Albumin	g/L	All	≤ 25	> 60	
Alkaline	U/L	All	Not applicable	\geq 3x NL	
phosphatase					
Total bilirubin	µmol/L	> 5d	Not applicable	≥ 34 *	
C-reactive	mg/L	All	Not applicable	≥ 10	
protein					
Total	mmol/L	All	Not applicable	≥ 6	
cholesterol					
Tryglicerides	mmol/l	All	Not applicable	≥ 1.9	
Creatinin	µmol/L	24m-11yr	Not applicable	≥100	
		12-18yr		≥120	
Glucose	mmol/L	24m-11yr	≤ 2.5	> 8	
		12-18yr	≤2.8	> 10	
GGT	U/L	All	Not applicable	\geq 3x NL	
Creatine kinase	U/L	> 3m	Not applicable	\geq 300	
LDH	U/L	All	Not applicable	≥ 700	
Urea nitrogen	Mmol/L	All	Not applicable	≥ 8.0	
Uric acid	µmol/L	6-11yr	Not applicable	≥ 500	
		12-19yr:			
		Μ		$\mathbf{M} \ge 600$	
		F		$\mathbf{F} \ge 500$	
Potassium	mmol/L	> 2m	3	≥6	
Sodium	mmol/L	All	≤130	≥ 150	
Calcium total	mmol/L	All	≤1.8	≥ 3	
Chloride	mmol/L	All	≤90	≥115	
Phosphorus,	mmol/L	4-11yr	≤ 0.9	≥ 2.8	
inorganic		12-15yr	≤ 0.9	≥ 2.5	
		16-19yr	≤ 0.6	≥ 2.2	
			≤ 0.6		

HEMOSTASIS AND COAGULATION						
Variable	Units	Age	Markedly Abnormal Criteria			
			Low	High		
Coagulation factor	% of normal	All	\leq 30	Not applicable		
VIII	ranges					
	U/dl	All	\leq 30			
Coagulation factor	% of normal	All	\leq 30	Not applicable		
IX	ranges					
	C C					
	U/dl	All	\leq 30			
Von Willebrand	VWF:RCo	All	≤ 20	Not applicable		
protein	activity(%)					
Fibrinogen	g/L	All	Not applicable	≥ 5		
Prothrombin Time	seconds	All	NA	≥ 20		
(PT)						
Partial	seconds	6 mo-18 yr	≤20	\geq 50		
Thromboplastin		-				
Time (APTT)						

* Applicable only for term healthy newborns

ECG					
Variable	Baseline Normal Value	Markedly Abnormal Treatment-			
	Normal value	Emergent value			
Duration of PR interval	3-8 yr: 90-160	3-8 yr ≥ 180 msec			
	9-16 yr: 90-180	9-16 yr \ge 200 msec			
Duration of QRS interval	3-8 yr: ≤ 100	$3-8 \text{ yr} \ge 110 \text{ msec}$			
	9-16 yr: ≤110	9-16 yr ≥120			
Duration of QTc interval	Not applicable*	\geq 450 msec			
Duration of QTc interval	Not applicable	Increase from baseline of ≥ 30 msec			

* We do not list a lower limit of normal but the literature often defines the short QT syndrome as a QTc < 300 ms.

PULSE RATE			
	Markedly Abnormal Criteria		
Age	Low	High	
7 years $\leq x < 9$ years	≤66	≥114	
9 years $\leq x < 11$ years	≤66	≥114	
11 years $\leq x < 13$ years girls	≤66	≥114	
11 years $\leq x < 13$ years boys	≤61	≥109	
13 years $\leq x < 15$ years girls	≤61	≥109	
13 years $\leq x < 15$ years boys	≤56	≥104	
15 years $\leq x < 17$ years girls	≤56	≥104	
15 years $\leq x < 17$ years boys	≤51	≥99	

RESPIRATORY RATE (breaths/min)			
	Markedly Abnormal Criteria		
Age	Low	High	
5 years $\leq x < 12$ years	≤10	≥40	
12 years $\leq x \leq 16$ years	_≤7	≥40	
$16 \text{ years} \leq x$	≤7	≥30	

Age	Unit	SBP	SBP	DBP	DBP
(years)		Lower	Upper limit	Lower	Upper
		limit (≤)	(≥)	limit (≤)	limit (≥)
8 years $\leq x < 9$ years	mm Hg	74	124	32	86
9 years $\leq x < 10$ years	mm Hg	76	125	33	87
10 years $\leq x < 11$ years	mm Hg	77	127	34	88
11 years $\leq x < 12$ years	mm Hg	79	129	35	89
12 years $\leq x < 13$ years	mm Hg	81	131	35	89
13 years $\leq x < 14$ years	mm Hg	84	134	36	90
14 years $\leq x < 15$ years	mm Hg	86	136	36	90
15 years $\leq x < 16$ years	mm Hg	89	139	37	91
16 years $\leq x < 17$ years	mm Hg	92	141	39	93

Markedly abnormal blood pressure levels for BOYS by age (height fixed at 50% percentile)

Markedly abnormal blood pressure levels for GIRLS by age (Height fixed at 50 % percentile)

Age	Unit	SBP	SBP	DBP	DBP
(years)		Lower	Upper	Lower	Upper
		limit (≤)	limit (≥)	limit (≤)	limit (≥)
8 years $\leq x < 9$ years	mm Hg	74	123	33	84
9 years $\leq x < 10$ years	mm Hg	76	124	34	85
10 years $\leq x < 11$ years	mm Hg	78	126	35	86
11 years $\leq x \leq 12$ years	mm Hg	80	128	36	87
12 years $\leq x < 13$ years	mm Hg	81	130	37	88
13 years $\leq x \leq 14$ years	mm Hg	83	132	38	89
14 years $\leq x \leq 15$ years	mm Hg	85	134	39	90
15 years $\leq x \leq 16$ years	mm Hg	86	135	40	91
16 years $\leq x \leq 17$ years	mm Hg	87	136	41	92

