#### 4 SELECTION OF TRIAL POPULATION

### 4.1 Trial Population

#### 4.1.1 Inclusion Criteria

Subjects who meet all of the following criteria will be eligible for the study:

- 1. Male or female, aged 9 years to 16 years, inclusive, being scheduled to undergo an elective colonoscopy
- 2. Females of childbearing potential must undergo a pregnancy test at screening and again at randomization
- 3. Subjects must have had ≥3 spontaneous bowel movements (SBM) per week for 1 month prior to the colonoscopy
- 4. Subjects should be willing, able, and competent to complete the entire procedure and to comply with study instructions
- 5. Written informed consent and assent obtained at screening

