### 7.2.3 Clinical Laboratory Variables

All laboratory measurements will be performed using appropriately validated methods by the study site's local laboratory. All sites should follow their local regulations for sample handling and storage.

Laboratory values will be reported to the investigator and sponsor (or the sponsor's representative) and will be entered into the eCRF database, which will be maintained by a clinical research organization selected by the Sponsor.

Out-of-range values will be described in the reference ranges to be provided by the local laboratory. Investigators will assess all out of range values as being either clinically significant or not clinically significant via the eCRF.

Sites will be specially instructed to review all laboratory results in order to determine if the subject is eligible for study participation, and to determine any AEs post study drug administration.

Samples will be collected during Visits 1, 3 and 4 for determination of the following test values:

- Hematology panel:
  - o Full complete blood count and differential
- Coagulation panel:
  - o Prothrombin time, activated partial thromboplastin time
- Full chemistry panel:
  - o Calculated creatinine clearance
  - o Serum magnesium (Mg++)
  - o Serum chemistry: glucose, blood urea nitrogen, potassium, sodium, chloride, calcium, total protein, albumin, total bilirubin, alkaline phosphatase, aspartate aminotransferase, alanine aminotransferase, bicarbonate and gamma glutamyl transferase
- Urinalysis panel

In addition, urine pregnancy tests will be performed at the local laboratory for female subjects of childbearing potential at Visits 1 and 2.

Trial Code: 000103 Date: 28-Jul-2014

E-Protocol Amendment-18395; Ver. 5

Supersedes: 4 Page 37 of 65

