10.3.2 Laboratory Variable Changes Relative to Normal Range

Changes relative to normal ranges will be presented with shift tables showing the total number of subjects, and number and percentage of subjects who experienced a shift from baseline. The following categories for shift tables are defined:

- Low: Values which are below the lower reference range limit;
- Normal: Values which are within the lower and upper reference range;
- High: Values which are above the upper reference range limit.

For all haematology and clinical chemistry variables, shift tables will be prepared to compare baseline values to the worst post-treatment value.

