10.3.3 Markedly Abnormal Changes

A summary table will be prepared that displays for each laboratory variable the number and percentage of subjects with normal baseline values who had at least one pre-specified markedly abnormal value anytime during the treatment period. The summary table will be presented by treatment group, overall and by age group. Pre-specified markedly abnormal criteria for laboratory tests are given in Appendix 1.

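### SAP 10.3.3 can count an unchanged, in-range laboratory value as markedly abnormal, and the Appendix 1 bilirubin limit, read literally, does not apply at ages 9-16

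*SAP*

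**What the plan says.** SAP 10.3.3 plans a table, for each laboratory variable, of children whose baseline is normal and who have at least one markedly abnormal value during the treatment period. The thresholds are fixed in advance: "Pre-specified markedly abnormal criteria for laboratory tests are given in Appendix 1". The section does not define a normal baseline. It also does not require the flagged value to be out of range or to have moved from baseline.

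SAP 10.3.2, the shift table, defines Normal as "Values which are within the lower and upper reference range". Those ranges are local. Protocol 7.2.3 states: "Out-of-range values will be described in the reference ranges to be provided by the local laboratory". Neither document prints a numerical range.

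Two Appendix 1 rows matter here:

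- Hematology: "Monocytes % 6 mo-18 yr NA 5", which means a high flag at 5% or more. Eosinophils (5%) and basophils (1%) are also given as percentages.
- Chemistry: "Total bilirubin µmol/L > 5d Not applicable ≥ 34", followed by an asterisk. A note printed after the coagulation table reads "Applicable only for term healthy newborns".

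The trial enrols: "Male or female, aged 9 years to 16 years, inclusive, being scheduled to undergo an elective colonoscopy". Protocol 7.2.3 includes both a differential count and total bilirubin at Visits 1, 3 and 4.

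**The concern.** A markedly abnormal limit should lie beyond the normal range. If a fixed limit lies inside it, two tables in the same report contradict each other: a child with the same in-range value before and after treatment is normal in one and markedly abnormal in the other. The incidence of abnormal laboratory findings is a secondary endpoint. With about 15 children per arm, a row filled largely by in-range values says little about the preparation.

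The bilirubin row raises a different problem. If its footnote means what it says, a variable that is measured at three visits has no usable threshold in a table promised for every laboratory variable.

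**Working it through.** The plan states no figure on this point, so there is nothing to reproduce. The check has three parts.

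**1. The counting rule applied to an unchanged value.** Take a child with monocytes at 7% before and after treatment, and assume a local upper limit of 8%. In 10.3.2 the child is normal at baseline and normal afterwards. In 10.3.3, taking normal baseline in the 10.3.2 sense, the child is counted because 7 ≥ 5. This happens for any local upper limit U above 5% and any unchanged value between 5% and U. Appendix 1 itself suggests this is not intended. ALT, AST, alkaline phosphatase and GGT are flagged only at three times a normal limit. The PR interval at 9-16 years is normal up to 180 and marked only from 200.

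**2. Size for monocytes.** All distributional inputs here are assumptions, because the documents give none.

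*(a) Share of in-range values at or above 5%.* Suppose the local range L to U is the central 95% of a normal distribution, so m = (L+U)/2 and s = (U−L)/3.92. Then share = [Φ((U−m)/s) − Φ((5−m)/s)] / 0.95. For 2-8%, m = 5, s = 1.53, and the share is (0.975 − 0.500)/0.95 = 0.50.

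| Assumed range | Share flagged | Of 15 |
|---|---|---|
| 0-4% or 0-5% | about 0 | 0 |
| 1-6% | 0.10 | 1.5 |
| 2-8% | 0.50 | 7.5 |
| 2-10% | 0.70 | 10.5 |
| 3-12% | 0.88 | 13.2 |

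*(b) Expected count per arm under the 10.3.3 rule with no drug effect.* Let baseline B and two post-dose values X1, X2 be normal with common mean 6, 7 or 8%, SD 1.5 or 2, and pairwise correlation 0.5. The count is 15 × P(B ≤ U and max(X1, X2) ≥ 5), by simulation. The last column repeats it with the added condition that the flagged value must exceed U.

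| Assumed U | Counted as written | Counted if also out of range |
|---|---|---|
| 5% | about 0-3 | about 0-3 |
| 6% | about 1-6 | about 1-4 |
| 8% | about 7-12 | about 2-4 |
| 12% | about 12-15 | fewer than 1 |

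At U = 5% the children counted have genuinely crossed the upper limit, so they are not in-range values. The low counts at 5-6% also reflect the baseline filter: with a mean of 6-8%, half or more of the children start above such a limit and drop out. If only one post-dose sample counts, the ranges are about 7-10 at 8% and 10-15 at 12%.

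**3. Matching the asterisks in Appendix 1.** The hematology asterisk sits on the basophil units and has its own note ("The percentage indicates the relative number of each type of leucocytes in the blood"). The ECG asterisk sits on the QTc row and also has its own note. The coagulation table has no asterisk. That leaves the newborn note for the only asterisk in the chemistry table, on bilirubin. The row's age entry covers anyone older than five days, and the note restricts it to newborns. The two cannot both govern a 9-16 year-old. Under the note, no child in this trial can be flagged for bilirubin.

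**The case against.** - **The monocyte effect rests on figures outside the documents.** This stands. If every local upper limit is 5% or lower, no in-range value above the limit exists to be flagged. Only the mechanism follows from the text, and the count must be given as a range.
- **Normal baseline might mean not meeting the Appendix 1 limit.** Then an unchanged value is never counted. Section 10.3.3 does not say which reading applies, and the only laboratory definition in the SAP is the one in 10.3.2. On the alternative reading, every child at 5% or more at baseline drops out, and a move from 4.9% to 5.0% counts as marked. The ambiguity needs closing either way.
- **Two post-dose samples may be too many.** SAP 10.3 limits treatment-emergent laboratory data to the residual time of drug effect, and Visit 4 falls 5 (±2) days after colonoscopy. With one sample the range for upper limits of 8-12% is still about 7-15 of 15.
- **The bilirubin note may be misplaced.** It is printed after another table, so the link to bilirubin is an inference. No other asterisk lacks a note, however, and the conflict with the age column remains until someone resolves it.
- **Other displays limit the harm.** This is correct. Each variable has its own row, and change from baseline, shift tables, out-of-range listings and the investigator's assessment of clinical significance are also planned. A reader might infer that a crowded monocyte row would hide a real signal in, say, sodium or potassium. The documents do not support that.

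**Conclusion.** The point holds as a minor but real defect in a descriptive safety table. As written, 10.3.3 can report unchanged in-range values as markedly abnormal wherever a fixed limit lies inside a local normal range. For monocytes this needs a local upper limit above 5%. Eosinophils at 5% and basophils at 1% are possible further cases, but nothing in the documents settles them. Under the stated assumptions about 7-15 of 15 children per arm are counted for upper limits of 8-12%, about 1-6 at 6% and about 0-3 at 5%.

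Three stronger readings are tempting and do not hold:

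- That nearly every child (84-100%, or 13-15 of 15) would be flagged. Those figures come from ignoring the normal-baseline condition that 10.3.3 imposes.
- That Appendix 1 as a whole does not suit this population. Many rows have age bands covering 9-16 years, and the liver enzyme limits are multiples of a normal limit.
- That the bilirubin entry over-counts. Read literally it leaves no applicable limit, so nobody is flagged. If the note is stray, nothing in the documents places 34 inside a normal range.

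**What to change.** In SAP 10.3.3, define normal baseline as within the local laboratory reference range, and add: *A value counts as markedly abnormal only if it meets Appendix 1 and also lies outside the local laboratory reference range.* In Appendix 1, reconcile the bilirubin footnote with its age column so that the limit applying at ages 9-16 is stated. Which limit that is remains for the sponsor to decide.

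The added condition makes 10.3.3 consistent with 10.3.2 for every row, without reviewing each limit against each site's range. It cannot add flags. It only removes in-range ones. The cost is a few lines of SAP text and one extra condition in the program. The shift tables already need the local ranges, so no new data are required.
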